**Phase:**

#### **Primary Objectives**

To determine the toxicity profile of an oral dose of calcitriol 45 mcg every other week (QOW) in patients at high risk of lung cancer.

**Overview of the Study Design:** The FDA has requested that a toxicity trial of calcitriol be completed in subjects without cancer using a 45 mcg dose at a lower frequency than was proposed in the previously approved Phase II lung cancer prevention trial. The FDA concerns focus on the lack of evidence of the safety of calcitriol in "healthy" patients who do not have cancer. However, the high risk lung cancer cohort at RPCI is comprised of patients with moderate to severe COPD. In order to document both the toxicity profile of calcitriol at this dose and frequency in high risk subject we have designed a Pilot study. This design incorporates a single-arm toxicity study of 20 patients.

In the proposed "Pilot single-armed pilot study" of 45 mcg of calcitriol, PO, QOW, dosing will continue for 3-months with a defined toxicity monitoring schedule outlined below. A total of 40 patients will be recruited from the High Risk Lung Cancer Screening Clinic and once screened and consented; they will be assigned to calcitriol (n=40). Once 20 patients on calcitriol have completed the 3-month treatment, an interim analysis of adverse events will be performed. Specific criteria for early stopping are outlined below. If the DSMB review of the interim analysis supports proceeding, the remaining 20 patients will be recruited into the trial. A follow-up bronchoscopy will be performed on all subjects after the end of the intervention period according to their routine follow-up schedule.

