**Primary Endpoints:**

To determine the number of patients with Grade III-IV toxicities or any Grade II toxicities *that last more than two weeks* associated with a 45 mcg dose of calcitriol administered every other week (QOW) in this population of patients at high risk of lung cancer.

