**Brief Statistical Section:**

We will test the null hypothesis that the proportion of grade 3-4 toxicities and grade 2 toxicities lasting more than 2 weeks will be 10% versus the one-sided alternative that the proportion of grade 3-4 toxicities will be greater than 10%. Given a sample size of n=40, assuming an alpha level 0.05, we will have 80% power to detect the proportion of toxicities of 15% or larger. An interim analysis will be performed after the first 20 subjects on calcitriol have completed the study. The study can be stopped early if the requirements of the null hypothesis (that this dose of calcitriol dose not result in an excess of DLT reports) are met that  $\leq 1$  toxicity is observed. After a full review of the data is completed by the DSMB the results will be reported to the FDA. Otherwise, the remaining 20 subjects on calcitriol will be recruited and treated at the end of the study period (3 months), at which point we will either reject the null hypothesis (if 8 or more toxicities are observed) or not reject the null hypothesis if 7 or less toxicities are observed.

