### 3. METHODS

#### 1. STUDY PURPOSES AND OBJECTIVES

The **Primary Hypothesis** for this study is that high-dose calcitriol 45 mcg. QOW will be well tolerated in a group of patients at high risk of lung cancer.

The **Primary Objectives** for this trial are as follows:

1. **To establish the safety of a 45 mcg dose of oral calcitriol QOW in non-cancer patients.** Forty patients from the RPCI high risk lung cancer cohort will be recruited to 45 mcg of oral calcitriol QOW (n=40) for a period of 3 months. All adverse events and serious adverse events will be reported to the FDA at the end of the study, regardless of relationship to the expected side effects of calcitriol. Patients will be on the study for 3 months. When the first 20 patients on calcitriol have completed the 3-month treatment, an interim analysis will be performed to determine the degree of dose-limiting toxicities associated with every other week administration.

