**Optimal Biologic Concentration Determination** - The optimal biologic concentration will be defined as the steady state concentration range that is associated with less than grade 2 toxicity and leads to target inhibition in 90% or greater of patients. Because there are inter-individual variations in absorption and metabolism of calcitriol, a more rational approach will be to evaluate the feasibility of relating concentrations of calcitriol rather than administered dose, to pharmacodynamic markers and toxicity. Thus, we will examine the relationship between exposure levels (Cp or AUC) of calcitriol with pharmacodynamic endpoints and polymorphisms in CYP24A1 and calcitriol metabolizing enzymes. Determining the strength and direction of the association between genotype(s), PD endpoints and calcitriol exposure levels will allow the construction of a preliminary model that will allow personalized dosing to a target drug exposure range (Cp or AUC) for validation in future chemoprevention studies. Based on these data, patients could be initially started on therapy on a non-toxic median dose that leads to target exposure levels. Eventually, doses could be adjusted during treatment to reach target concentrations, as is done with other drugs that have narrow therapeutic indexes such as vancomycin and busulfan for bone marrow transplantation.

We will test the null hypothesis that the proportion of grade 3-4 toxicities or grade 2 toxicities that persist more than two weeks will be 10% versus the one-sided alternative that the proportion of these toxicities will be greater than 10%. An interim analysis will be performed after the first 20 subjects on calcitriol have completed the study. The study can be stopped early at the interim point and the null hypothesis will not be rejected if  $\leq 1$  toxicity is observed, at which time the DSMB will summarize the findings and the results, including all toxicity reports will be submitted to the FDA. Otherwise, the full 40 subjects will be recruited into the study. At the end of the study period, we will again either reject the null hypothesis (if 8 or more DLT toxicities are observed) or not reject the null hypothesis if 7 or less toxicities are observed.

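### The protocol conflicts on whether DSMB support is needed to enrol the second 20 patients, and its readable text gives no interim boundary for excess toxicity

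*Combined protocol and SAP*

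**What the plan says.** Three places in the combined protocol and SAP describe what follows the interim look.

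- **Abstract, Overview of the Study Design:** "If the DSMB review of the interim analysis supports proceeding, the remaining 20 patients will be recruited into the trial". No count is attached. The same paragraph says "Specific criteria for early stopping are outlined below".
- **Abstract, Brief Statistical Section:** an early stop is possible at 1 toxicity or fewer. Then: "Otherwise, the remaining 20 subjects on calcitriol will be recruited and treated at the end of the study period". No upper limit and no DSMB condition.
- **Section 12:** "The study can be stopped early at the interim point and the null hypothesis will not be rejected if" at most 1 toxicity is observed. Then: "Otherwise, the full 40 subjects will be recruited into the study". At the end, "we will again either reject the null hypothesis (if 8 or more DLT toxicities are observed"; 7 or fewer means no rejection.

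In both statistical passages the DSMB appears only in the branch for 1 or fewer, where it reviews or summarises the results.

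The Primary Endpoints paragraph counts patients: "To determine the number of patients with Grade III-IV toxicities or any Grade II toxicities" lasting more than two weeks. Section 3 times the look by completion of treatment: "When the first 20 patients on calcitriol have completed the 3-month treatment, an interim analysis will be performed". Section 5.0 and Section 11.2.3 remove individual patients with qualifying toxicity. Section 10 has the DSMB review adverse events and interim analyses. Section 11.4 sets expedited FDA reporting. None of these gives a trial-level count.

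**The concern.** At 2 or more of 20, the design overview requires DSMB support before recruitment resumes, while the two statistical passages direct recruitment without it. A DSMB looking at, say, 6 of 20 cannot tell from the text whether it may halt accrual, or how the null hypothesis would be reported if it did.

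The overview promises stopping criteria, but the only count that follows in the readable text stops the trial when toxicity is rare. None applies when toxicity is frequent. Toxicity is the sole primary question, and the trial was designed to answer an FDA concern about safety in people without cancer. Taken literally, the statistical passages enrol 20 more such people even when their results can no longer change the hypothesis test.

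**Working it through.** **Inputs.** From Section 12 and the Brief Statistical Section: null rate 10%, one-sided alpha 0.05, n = 40, interim at 20, stop at ≤1, reject at ≥8 of 40. The documents give no expected rate for this endpoint, so a range is shown. X1 and X2 are the numbers of affected patients in the first and second 20, each Binomial(20, p).

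**The plan's own figures.** P(≥8 of 40 | 10%) = 0.0419 and P(≥7 of 40 | 10%) = 0.0995, so 8 is the smallest cut-off that keeps alpha within 0.05. The stated 80% power at 15% does not reproduce: the exact value is 0.244, or 0.241 with the interim stop. That is a separate matter. The power illustrations below use 25%, where the rule does have about 80% power.

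**Rule as written.** Rejection probability = Σ over x = 2 to 20 of P(X1 = x) × P(X2 ≥ max(0, 8 − x)). This gives 0.0412 at 10%, 0.2408 at 15%, 0.8132 at 25% and 0.9419 at 30%.

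**Interim count of 8 or more.** If X1 ≥ 8 then X1 + X2 ≥ 8 whatever X2 is, so rejection is certain at any true rate. Stopping accrual and rejecting there leaves every rejection probability above identical.

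**Expected sample size.** As written it is 20 + 20 × P(X1 ≥ 2). With a boundary at 8 it is 20 + 20 × P(2 ≤ X1 ≤ 7). The saving is 20 × P(X1 ≥ 8). At 25%, P(X1 ≤ 1) = 0.024 and P(X1 ≥ 8) = 0.102, so the two values are 20 + 20 × 0.976 = 39.5 and 20 + 20 × 0.874 = 37.5.

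| True rate | P(X1 ≥ 8) | Expected n, as written | Expected n, boundary at 8 | Saving |
|---|---|---|---|---|
| 15% | 0.6% | 36.5 | 36.4 | 0.1 |
| 20% | 3.2% | 38.6 | 38.0 | 0.6 |
| 25% | 10% | 39.5 | 37.5 | 2.0 |
| 30% | 23% | 39.8 | 35.3 | 4.6 |
| 40% | 58% | 40.0 | 28.3 | 11.7 |

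At the null rate of 10%, P(X1 ≥ 8) is 0.04%. The table assumes that the interim counts the first 20 treated patients and that nobody beyond 20 is enrolled before the result is known.

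**Denominator.** If the interim waits for 20 completers, and patients with a qualifying toxicity are removed and so do not complete, then about 20/0.75 = 27 patients are enrolled by then at 25%, and 20/0.60 = 33 at 40%. At most about 13 or 7 would remain to be enrolled, instead of 20, and the saving shrinks accordingly.

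**DSMB halt at 2 to 7 without rejection.** Each such count removes P(X1 = x) × P(X2 ≥ 8 − x) from the power. At 25% and x = 7 that is 0.1124 × 0.9968 = 0.112, and 0.813 − 0.112 = 0.701.

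| Counts at which the DSMB halts | Power at 25% | Type I error |
|---|---|---|
| none | 0.81 | 0.0412 |
| 7 | 0.70 | 0.0395 |
| 6–7 | 0.54 | 0.0341 |
| 5–7 | 0.35 | 0.0238 |
| any of 2–7 | 0.10 | 0.0004 |

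The range 2 to 7 holds 61% of interim outcomes at a true 10% and 87% at 25%, so the unclear zone is the likely one.

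**The case against.** The case on the other side has four parts.

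**The texts can be read together.** The statistical passages give the test and the overview adds DSMB review; nothing removes the DSMB's authority. A reader might infer that the DSMB is barred from halting, or that nobody is watching. The documents do not support that: affected patients are removed, the DSMB evaluates all adverse events, and a clinically important rise in serious related events is reportable to the FDA within 15 days. What stands is that the plan does not say which text governs at 2 or more, or what a halt means for the test.

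**A boundary may exist in the schema.** The schema is not shown and lies after the sentence promising criteria. This stands: the absence can be asserted only of the readable text.

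**The boundary at 8 matters little.** It is rarely reached at low rates, and the second 20 would still inform the toxicity profile and the PK/PD model. This also stands, and it makes the boundary a trade-off rather than a correction of error rates. Continuing at 2 to 7 is ordinary two-stage behaviour and is not criticised here.

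**The denominator is not settled.** The look is timed by completion, yet patients with qualifying toxicity are removed. The savings therefore hold only under the stated assumption. Certainty of rejection once 8 patients are affected does not depend on it, provided removed patients count in the final total.

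**Conclusion.** The concern holds, and the conflict between the design overview and the two statistical passages is its firmer part. It should be fixed because it leaves the DSMB's role undefined over the most likely interim results, and one possible reading costs between 0.11 and 0.71 of the 0.81 power at a true 25%.

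The missing upper boundary is a smaller matter: negligible at 15%, about 2 patients on average at 25%, and large only at rates near 40%. It does not inflate type I error or reduce power, and a reader should not infer that it does. Whether the stop at 1 or fewer is binding hardly matters: alpha is 0.0412 if it is always used and 0.0419 if it never is.

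These conclusions count patients rather than events, as the Primary Endpoints paragraph does, and treat the final count as cumulative over all 40.

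**What to change.** 1. **Reconcile the three passages.** State whether the branch for 2 or more of 20 is subject to DSMB support. If the DSMB may halt at 2 to 7, state how the null hypothesis is then reported and give the power consequence. No view is taken here on what discretion the DSMB should have.
2. **Define the interim denominator** as all treated patients, including those removed for toxicity.
3. **Inexpensive improvement.** Add to the Brief Statistical Section and Section 12 that if 8 or more patients have had a qualifying toxicity by the interim, no further patients are accrued and the null hypothesis is rejected. This is the plan's own final cut-off. No rule is proposed for patients still on treatment.

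**Cost.** The drafting is short, but items 1 and 2 need decisions from the sponsor and the DSMB. Item 3 leaves alpha, power and maximum n unchanged. Its price is less information when toxicity is high. There are fewer patients for the toxicity profile and PK/PD model, and the interval is wider (exact 95% interval 19–64% for 8 of 20, against 25–57% for 16 of 40). The raw proportion is also slightly biased upward (mean 25.7% at a true 25%, 42.2% at 40%).

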#### **Sample Size Calculations:**

Given a sample size of n=40, we will 80% power be able to detect the proportion of toxicities of 15% or larger different from 10%, assuming an alpha level 0.05.

I 90206 Amendment # 18

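### The primary endpoint counts patients, but the hypotheses, both cut-offs and the power statement count toxicities, and nothing says that each patient counts once

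*Combined protocol and SAP*

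**What the plan says.** Under Primary Endpoints in the abstract, the aim is "To determine the number of patients with Grade III-IV toxicities or any Grade II toxicities" lasting beyond two weeks. The unit is the patient.

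Section 12 changes the unit:

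- **Null:** "the proportion of grade 3-4 toxicities or grade 2 toxicities that persist more than two weeks will be 10"%, against a one-sided alternative of more than 10%.
- **Interim rule, after 20 subjects:** the study can stop without rejection if at most one "toxicity is observed, at which time the DSMB will summarize the findings".
- **Final rule:** "reject the null hypothesis (if 8 or more DLT toxicities are observed) or not reject the null hypothesis if 7 or less toxicities are observed".
- **Power (Sample Size Calculations):** 80% power with n=40 and alpha 0.05 to "detect the proportion of toxicities of 15% or larger".

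The abstract's Brief Statistical Section repeats the event wording of the final rule ("reject the null hypothesis (if 8 or more toxicities are observed"). It tests the null "versus the one-sided alternative that the proportion of grade 3-4 toxicities will be greater than 10"%, which leaves out the persistent grade 2 events that Section 12 includes. The design overview says that after 20 patients "an interim analysis of adverse events will be performed".

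The term DLT in the final rule is not defined for this trial. In Section 9, under Risks Warranting Further Discussion, it refers to hypercalcemia, which is narrower than the endpoint.

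**The concern.** A count of patients and a count of toxicities agree only if no patient contributes more than one qualifying toxicity, or if the plan says that each patient counts once. The plan does not say so.

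The cut-offs are small (1, 7 and 8), so one patient with two events can change a decision that goes to the DSMB and the FDA. The binomial calculation behind a cut-off of 8 in 40 also assumes at most one count per subject. Once events are counted, that calculation no longer guarantees alpha at or below 0.05.

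Two further gaps lie in the same sentences. The endpoint and hypotheses name grades 3 and 4 only, so a fatal toxicity is literally outside the count, although the Toxicity Monitoring paragraph of Section 5.0 covers grade 3 and above without an upper limit. The decision rule also does not say whether events count whatever their cause.

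**Working it through.** **Inputs from the documents.** n = 40 subjects in one arm; null rate 10%, one-sided; nominal alpha 0.05; optional stop at 1 or fewer after 20 subjects; rejection at 8 or more.

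**Input not in the documents.** The mean number of qualifying toxicities per affected patient. It is assumed here to be 1 + λ, with λ = 0.05 or 0.10.

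**Step 1: reproduce the cut-off, counting patients.** Let X ~ Binomial(40, 0.10).

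- P(X ≥ 8) = 0.0419.
- P(X ≥ 7) = 0.0995.

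So 8 is the smallest cut-off with alpha at or below 0.05. If the interim stop is always taken, let X1 and X2 be the counts in the two halves of 20. Then P(reject) = Σ P(X1 = x)·P(X2 ≥ 8 − x) over x from 2 to 20 = 0.0412. The chance of stopping is P(X1 ≤ 1) = 0.9^20 + 20·0.1·0.9^19 = 0.1216 + 0.2702, about 0.392.

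**Step 2: where the two counts part.**

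- *Final rule:* six affected patients, two of whom have two concurrent toxicities each, give 4 + 2·2 = 8 toxicities. The event rule rejects. The patient rule (6, below 8) does not.
- *Interim rule:* one affected patient among 20, with two concurrent toxicities, gives 2 toxicities. The event rule does not allow the stop. The patient rule (1) does.

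**Step 3: size of the effect when null and cut-offs are both read as events.** The null is then 0.10 toxicities per patient, so the proportion of patients affected is p = 0.10/(1 + λ). In each half, K ~ Binomial(20, p) patients are affected and the number of toxicities is K + Poisson(λK). The two halves are combined by exact convolution.

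| Events per affected patient | p | P(reject), stop binding | P(reject), no stop | P(stop at interim) |
|---|---|---|---|---|
| 1 (each patient once) | 0.1000 | 0.0412 | 0.0419 | 0.392 |
| 1.05 | 0.0952 | 0.0496 | 0.0509 | 0.406 |
| 1.10 | 0.0909 | 0.0568 | 0.0589 | 0.418 |

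Allowing at most one extra toxicity per affected patient gives nearly the same result: 0.0493 and 0.0561 with the stop, 0.0507 and 0.0580 without. P(reject) passes 5% at a mean of about 1.045 without the stop and 1.053 with it.

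**Step 4: the power statement.** Counting patients, P(X ≥ 8) at a true rate of 15% is 0.244. Correcting the unit does not bring the rule near 80%.

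**The case against.** The case for leaving the text alone is strong on intent. The one section headed as the endpoint says patients. A 10% proportion with n = 40 has no natural denominator except patients, and the cut-off of 8 is the patient-level one. Patients are removed after a qualifying toxicity (Sections 5.0 and 11.2.3), which limits repeats. The interim wording about adverse events describes a safety review and sets no counting rule. The abstract glosses the null as no excess of DLTs, so the term presumably means the tested toxicities. Counting events errs towards flagging harm, and missing the interim stop only means enrolling the planned 40.

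Most of this stands and limits the weight of the point. It does not remove it, because intent is not a counting rule. Removal does not prevent concurrent toxicities, and adverse events are collected until 30 days after the last intervention (Section 11.1). Concurrent events are plausible: Section 5.0 lists dehydration, constipation, nausea and vomiting together as consequences of high calcium.

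A reader might infer a larger error. If 10% of patients are affected while toxicities are counted against the cut-off, P(reject) is 6.2% to 8.4% at the same assumed means, with the stop binding. No passage states that mixture. Section 12 words the null and the cut-offs alike as toxicities, so the literal reading is the one in Step 3.

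**Conclusion.** The mismatch is real and should be corrected, but its numerical effect is modest. Counting each patient once, the rule has exact alpha 0.0419, or 0.0412 if the stop is always taken. Read literally as events throughout, it gives about 5.0% to 5.7% with a binding stop and 5.1% to 5.9% without. Those ranges rest on an assumed 1.05 to 1.1 events per affected patient. With fewer multiple events, alpha stays under 0.05.

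The documents do not support saying that the trial's alpha is seriously inflated or that its sponsor means to count events. Nor do they support saying that the wording hides toxicity: the error runs towards declaring an excess. Nor does the event wording necessarily make the interim stop less likely. With the null also on events, its probability rises slightly, from 39.2% to between 40.6% and 41.8%.

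What remains is a decision rule that does not match its endpoint and that can turn on one patient.

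**What to change.** 1. In the Brief Statistical Section and Section 12, state the null, the alternative and both cut-offs as the number or proportion of patients with at least one qualifying toxicity as defined under Primary Endpoints, each patient counted once: at most 1 of 20 at the interim, at least 8 of 40 at the end.
2. Make the abstract's alternative include persistent grade 2 events, as Section 12 does.
3. Replace DLT in the rule with this event.
4. State whether the count is made irrespective of attribution.
5. State that a grade 5 toxicity counts. This is a small change to the endpoint itself, not only to its wording.
6. In Sample Size Calculations, write proportion of patients. The 80% power at 15% needs separate correction, since exact power is 24.4%.

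Separately, the first removal criterion in Section 5.0 is limited to events attributed to the drug, while the Toxicity Monitoring paragraph in the same section and the removal text in Section 11.2.3 apply whatever the cause. These passages must be reconciled.

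The cost is a text amendment. The cut-offs, the sample size and the data collected do not change.

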#### **Sample Size Calculations:**

Given a sample size of n=40, we will 80% power be able to detect the proportion of toxicities of 15% or larger different from 10%, assuming an alpha level 0.05.

I 90206 Amendment # 18

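### The claimed 80% power at a 15% toxicity rate is wrong: with 40 patients and a cut-off of 8, power at 15% is about 24%, and 80% is reached only near 25%

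*Combined protocol and SAP*

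**What the plan says.** The hypothesis, the decision rule and the power claim appear twice, in the Brief Statistical Section of the abstract and in Section 12 (Statistical Analysis).

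- **Hypotheses:** a toxicity proportion of 10% against a one-sided alternative above 10%. A toxicity counts if it is grade 3-4, or grade 2 lasting more than two weeks.
- **Interim:** after 20 patients, the study can stop without rejecting the null if there is at most 1 toxicity.
- **Final rule, after 40 patients:** "reject the null hypothesis (if 8 or more DLT toxicities are observed) or not reject the null hypothesis if 7 or less toxicities are observed".
- **Power, Section 12, Sample Size Calculations:** "80% power be able to detect the proportion of toxicities of 15% or larger different from 10%, assuming an alpha level 0.05", with n=40.
- **Power, abstract:** "we will have 80% power to detect the proportion of toxicities of 15% or larger", also with n=40 and alpha 0.05.

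There is no other justification of the sample size.

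**The concern.** Forty patients cannot separate 15% from 10% with 80% power. The expected counts are 6 and 4, and the rule needs 8. Even at a true rate of 15%, the expected count falls two short of the cut-off.

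This matters because safety is the only primary objective. The Overview of the Study Design says the trial exists because the FDA asked for toxicity data in subjects without cancer, and the Background makes those data the basis for a later placebo-controlled trial with weekly dosing. Failure to reject is the favourable outcome here, so power is the probability of catching excess toxicity. A reader who believes the stated figure would take 7 or fewer events in 40 as good evidence against a 15% rate. The error runs towards false reassurance.

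**Working it through.** **Inputs.** n = 40, null rate 10%, one-sided alpha 0.05, rejection at 8 or more, interim stop at 1 or fewer of the first 20. All are in Section 12 and the abstract's Brief Statistical Section. Each patient is counted once, as with or without a qualifying toxicity; the Primary Endpoints entry in the abstract supports this, since it counts patients. All 40 are taken as evaluable.

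**Step 1: does the cut-off match alpha?** With X ~ Binomial(40, p), type I error is P(X ≥ c | p = 0.10).

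- c = 7: 0.0995
- c = 8: 0.0419

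So 8 is the smallest cut-off with exact one-sided error below 0.05. The rule itself is sound.

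**Step 2: can 80% at 15% be reproduced?** Power is P(X ≥ 8 | p = 0.15) = 0.2441, so it cannot. Other methods at n = 40, 15% and alpha 0.05 give:

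| Method | Power at 15% |
|---|---|
| Normal approximation, one-sided | 31.0% |
| Same, continuity-corrected | 23.6% |
| Wald, one-sided | 22.4% |
| Arcsine, one-sided | 24.7% |
| Normal approximation, two-sided | 22.3% |

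The first row, for example, is Φ[(0.05 − 1.645·√(0.09/40)) / √(0.1275/40)] = Φ[(0.05 − 0.0780)/0.0565] = Φ(−0.496) = 0.310. Raising one-sided alpha to 0.20 brings the normal approximation only to 57%. Reaching 80% power at 15% with 40 patients would require rejecting at 4 or more, with a type I error of 58%.

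**Step 3: power of the plan's rule, without and with the interim stop.** With the stop, power is the sum over x = 2,…,20 of P(X₁ = x)·P(X₂ ≥ 8 − x), where X₁ and X₂ are independent Binomial(20, p).

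| True rate | Fixed n = 40 | With interim stop |
|---|---|---|
| 10% (type I error) | 4.19% | 4.12% |
| 15% | 24.4% | 24.1% |
| 20% | 56.3% | 55.7% |
| 25% | 81.8% | 81.3% |

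Solving for 80% power gives a true rate of 24.5% (fixed) or 24.7% (with the stop). The interim rule costs less than one percentage point of power at each of these rates.

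**Step 4: what 80% power at 15% would need.** The normal approximation gives n = [(1.645·√0.09 + 0.842·√0.1275)/0.05]² = (0.794/0.05)² ≈ 252. By exact binomial, the first n that reaches 80% is 270, rejecting at 36 or more (type I error 4.7%, power 80.1%). That is nearly seven times the planned 40.

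**The case against.** The best defence is that the Section 12 sentence is garbled rather than miscalculated. Its wording, 15% or larger different from 10%, can be read as a difference of 15 percentage points, that is, 25% against 10%. On that reading n = 40, alpha 0.05, the cut-off of 8 and roughly 80% power all fit together (81.8%, or 81.3% with the interim stop). That may well be where the statement came from. It does not save the text. The abstract drops the words about a difference and names a proportion of 15%, so it is wrong on any method, and Section 12 is at best ambiguous.

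It can also be said that this is a pilot, that the decision rule is explicit with a valid type I error, and that no step of conduct or analysis uses the 80% figure. All true, and a small pilot is acceptable. But the plan chose a formal test with stated error rates, and the stated power is how a reader will judge a null result.

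Two smaller points stand as qualifications. The rule counts toxicities, not patients, so the calculation depends on one outcome per patient. And rewording is enough only if 25% is an acceptable target. If the sponsor needs to detect 15%, 40 patients will not do.

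**Conclusion.** The power statement is wrong as written. At a true rate of 15% the plan's own rule has 24% power, about 56 points below the claim; a 15% rate passes undetected about 76% of the time and a 20% rate about 44%. The rate detectable with 80% power is about 25%. The sample size, the cut-off and the type I error are consistent with each other; only the stated power, or the rate attached to it, fails. These figures assume one binary outcome per patient and 40 evaluable patients. The Sample Size Calculations section makes no allowance for dropout, and with the cut-off held at 8, fewer evaluable patients would lower power further.

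**What to change.** In both the Brief Statistical Section of the abstract and Sample Size Calculations in Section 12, delete the claim of 80% power at 15% and state the real operating characteristics, for example:

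> With 40 patients and rejection of the null hypothesis at 8 or more patients with a qualifying toxicity, the exact one-sided type I error is about 4.1% and power is about 81% if the true rate is 25%. Power is about 56% at 20% and about 24% at 15%. These figures include the interim stopping rule.

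The text should say that the count is of patients, in line with the primary endpoint. The sample size, cut-off and interim rule are unchanged. The cost is wording in two places and a less favourable stated detectable rate, 25% in place of 15%. In making the change the sponsor should confirm that 25% is the intended alternative; keeping 15% with 80% power would be a different design, at about 270 patients.
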